7.3.2 Anticipated Toxicities

All anticipated toxicities are listed in the informed consent document.

7.3.3 Toxicity Reporting

The research team and the treating physicians/Principal Investigator will review the toxicities and record them in OnCore. Attribution of toxicity to protocol and clinical relevance will be reviewed.

If a dose limiting toxicity (DLT) or other significant medical event is unexpected and probably related to study treatment, then it will be submitted to the UAB IRB via the Problem Report form. All adverse events entered into OnCore will be submitted for review on an annual basis.

Patients that are withdrawn from the study after beginning protocol treatment will be followed for adverse events for 30 days after last dose of glyburide or investigational medication.

7.3.4 Grading Toxicities and Adverse Events

The descriptions and grading scales found in the revised NCI Common Terminology Criteria for Adverse Events (CTCAE) version 4.0 will be utilized for adverse event reporting on this study. The CTCAE version 4.0 is located on the CTEP website at http://ctep.cancer.gov/protocolDevelopment/electronic_applications/ctc.htm. See Appendix VII for Adverse Event (AE) definitions and grading scale information.

PILOT PORTION

If multiple toxicities are seen, the presence of a DLT should be based on the most severe toxicity experienced. Any patient who achieves a DLT will be taken off of glyburide immediately, but will still be evaluable.

Concerning Toxicity

1. Any asymptomatic grade 3 or 4 hypoglycemia as defined by CTCAE version 4.0.
2. Any non-hematologic grade 3 or greater toxicity (including neurologic toxicity) that is associated with a blood glucose level ≤ 80 mg/dl and is resolved with “low blood

sugar intervention" (e.g. a return of blood glucose level to ≥ 80 mg/dl). See **Section 5.4.1.1 for a List of Low Blood Sugar Interventions.**

Serious Toxicity

3. Any grade 5 toxicity that is deemed by the investigator to be at least possibly attributable to glyburide.
4. Any symptomatic grade 3 or 4 hypoglycemia associated with a non-hematologic grade 3 or greater toxicity that is not resolved with "low blood sugar intervention" (e.g. does not return to blood glucose level to ≥ 80 mg/dl) that is deemed by the investigator to be at least possibly attributable to glyburide. **See Section 5.4.1.1 for a List of Low Blood Sugar Interventions.**

Glyburide will be discontinued for any patient that meets the criteria for either a "**concerning toxicity**" or "**serious toxicity**". These patients will still be evaluable.

Any "**concerning toxicity**" that is observed in at least 6 (of 10 evaluable) patients will trigger a dose reduction (see section 7.1). After 1 dose reduction, if at least 6 (of 10 evaluable) patients are observed to have a "**concerning toxicity**", the study will be terminated.

Any "**serious toxicity**" that is observed in at least 1 (of 10 evaluable) patients will trigger a dose reduction. After 1 dose reduction, if at least 1 (of 10 evaluable) patients is observed to have a "**serious toxicity**", the study will be terminated.

RANDOMIZED PORTION

If multiple toxicities are seen, the presence of a DLT should be based on the most severe toxicity experienced. Any patient who achieves a DLT will be taken off of the investigational medication immediately, but will still be evaluable.

Concerning Toxicity

1. Any asymptomatic grade 3 or 4 hypoglycemia as defined by CTCAE version 4.0
2. Any non-hematologic grade 3 or greater toxicity (including neurologic toxicity) that is associated with a blood glucose level ≤ 80 mg/dl and is resolved with "low blood sugar intervention" (e.g. a return of blood glucose level to ≥ 80 mg/dl).**See Section 5.4.1.1 for a List of Low Blood Sugar Interventions.**

Serious Toxicity

3. Any grade 5 toxicity that is deemed by the investigator to be at least possibly attributable to the investigational medication.
4. Any symptomatic grade 3 or 4 hypoglycemia that is associated with a non-hematologic grade 3 or greater toxicity that is not resolved with "low blood sugar intervention" (e.g. does not return to blood glucose level of ≥ 80 mg/dl) that is deemed by the investigator to be at least possibly attributable to the investigational medication. **See Section 5.4.1.1 for a List of Low Blood Sugar Interventions.**

Investigational medication will be discontinued for any patient that meets the criteria for a ***“concerning toxicity” or “serious toxicity”***. These patients will still be evaluable. All other patients currently on treatment at the time may continue with their current investigational medication without interruption.

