4.1.9 Conditions for early patient stopping of glyburide

- 4.1.9.1** A dose limiting toxicity (DLT) is reached. See section 5.3.1.
- 4.1.9.2** Patient requires corticosteroid administration after registration but prior to SRS, please note these patients will be deemed inevaluable.

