Appendix VII for Adverse Event (AE) definitions and grading scale information.

If multiple toxicities are seen, the presence of a DLT should be based on the most severe toxicity experienced. Any patient who achieves a DLT will be taken off of glyburide immediately, but will still be evaluable.

Concerning Toxicity

1. Any **asymptomatic grade 3 or 4 hypoglycemia** as defined by CTCAE version 4.0.
2. Any **non-hematologic grade 3 or greater toxicity** (including neurologic toxicity) that is associated with a blood glucose level ≤ 80 mg/dl and is resolved with “low blood sugar intervention” (e.g. a return of blood glucose level to ≥ 80 mg/dl). **See Section 5.4.1.1 for a List of Low Blood Sugar Interventions.**

Serious Toxicity

1. Any **grade 5 toxicity** that is deemed by the investigator to be **at least possibly attributable to glyburide**.
2. Any **symptomatic grade 3 or 4 hypoglycemia associated with a non-hematologic grade 3 or greater toxicity** that is not resolved with “low blood sugar intervention” (e.g. does not

return to blood glucose level to ≥ 80 mg/dl) that is deemed by the investigator to be at least possibly attributable to glyburide. **See Section 5.4.1.1 for a List of Low Blood Sugar Interventions.**

Glyburide will be discontinued for any patient that meets the criteria for either a "**concerning toxicity**" or "**serious toxicity**". These patients will still be evaluable.

Any "**concerning toxicity**" that is observed in at least 6 (of 10 evaluable) patients will trigger a dose reduction (see section 7.1). After 1 dose reduction, if at least 6 (of 10 evaluable) patients are observed to have a "**concerning toxicity**", the study will be terminated.

Any "**serious toxicity**" that is observed in at least 1 (of 10 evaluable) patients will trigger a dose reduction. After 1 dose reduction, if at least 1 (of 10 evaluable) patients is observed to have a "**serious toxicity**", the study will be terminated.

5.3.1.1 If a dose reduction should occur, it will occur once the pre-specified DLT is reached.

Glyburide will be reduced to 0.75 mg po BID. In the event this dose reduction should occur, the Pilot Portion will be performed using the reduced dose (e.g. 10 evaluable patients are required to be assessed). If another DLT is observed at the reduced glyburide dose warranting a dose reduction, the study will be terminated.

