5.3.1.2 The patient who experiences a DLT (e.g. either a "**concerning toxicity**" or "**serious toxicity**") will stop glyburide immediately, but will still be evaluable. If the DLT is a "**concerning toxicity**", all other patients currently on treatment at the time may continue at their current glyburide dose. If the DLT is a "**serious toxicity**", all other patients currently on treatment will either be dose reduced immediately (if on full dose glyburide) or stop glyburide immediately (if on reduced dose glyburide). All other patients will still be evaluable.

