5.4.2 Randomized Portion

5.4.2.1 All patients will be provided with a medication/blood glucose log, a blood glucose monitor, and taught to perform self fingerstick glucose draws (see Appendices II-VI). The first blood glucose draw will be done by a nurse or research team member on the visit 5-9 days prior to SRS and the initial value will be recorded in the blood glucose log.

5.4.2.2 If the Pilot Portion (at either full dose or at one dose reduction) demonstrates no "**serious toxicities**" and ≤ 3 "**concerning toxicities**" (described in section 5.3.1), patients in the Randomized Portion of the trial will be taught and instructed to measure blood glucose levels once a day (in the morning before breakfast (fasting)) starting at the initiation of the investigational medication and continuing for at least the first week after SRS. If no "**concerning toxicities**" or "**serious toxicities**" are found at the one week post SRS visit, then the patient may proceed through the rest of the trial with no further need to assess blood glucose via the fingerstick draws. If the patient does experience a "**concerning toxicity**" or "**serious toxicity**" then he/she must discontinue their investigational medication (as per section 5.3.2) and will not have to continue checking their blood glucose levels.

5.4.2.3 If the Pilot Portion (at either full dose or at one dose reduction) demonstrates no "**serious toxicities**" and 4-5 "**concerning toxicities**" (described in section 5.3.1), patients in the Randomized Portion of the trial will be taught and instructed to measure blood glucose as per section 5.4.1.

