APPENDIX VII
CTCAE version 4.0 and Toxicity Criteria

This study will utilize **NCI Common Terminology Criteria for Adverse Events (CTCAE) version 4.0 for toxicity and Adverse Event Reporting**. A **grading** (severity) scale is provided for each Adverse Event (AE) term. A copy of the CTCAE version 4.0 can be downloaded from the CTEP web site at: http://ctep.cancer.gov/protocolDevelopment/electronic_applications/ctc.htm. All investigators and study staff have access to a copy of the CTCAE version 4.0. Also, see Sections 5.3 and 7.3 for additional information.

An **Adverse Event (AE)** is any unfavorable and unintended sign (including an abnormal laboratory finding), symptom, or disease temporally associated with the use of a medical treatment or procedure that may or may not be considered related to the medical treatment or procedure.

Grade refers to the severity of the AE. The CTCAE displays Grades 1 through 5 with unique clinical descriptions of severity for each AE based on this general guideline:

- **Grade 1:** *Mild; asymptomatic or mild symptoms; clinical or diagnostic observations only; intervention not indicated.*
- **Grade 2:** *Moderate; minimal, local or noninvasive intervention indicated; limiting age-appropriate instrumental Activities of Daily Living (ADL).*
- **Grade 3:** *Severe or medically significant but not immediately life-threatening; hospitalization or prolongation of hospitalization indicated; disabling; limiting self care Activities of Daily Living (ADL).*
- **Grade 4:** *Life-threatening consequences; urgent intervention indicated.*
- **Grade 5:** *Death related to AE.*

Adverse Event	GRADE				
	1	2	3	4	5
Hypoglycemia	<LLN – 55mg/dL; <LLN – 3.0 mmol/L	<55-40 mg/dL; <3.0-2.2 mmol/L	<40-30 mg/dL; <2.2-1.7 mmol/L	<30 mg/dL; <1.7 mmol/L; life-threatening consequences; seizures	Death

Definition: A disorder characterized by laboratory test results that indicate a low concentration of glucose in the blood.

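### Grade 3-4 hypoglycemia is always a DLT when it is asymptomatic, but some symptomatic events below 40 mg/dl count nowhere

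*Combined protocol and SAP*

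**What the plan says.** The DLT definitions appear four times with the same structure: 5.3.1 and the pilot part of 7.3.4, and 5.3.2 and the randomized part of 7.3.4. Both concerning and serious toxicities are DLTs.

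- **Concerning, item 1:** "Any asymptomatic grade 3 or 4 hypoglycemia as defined by CTCAE version 4.0". Nothing is required about resolution, attribution or an accompanying toxicity.
- **Concerning, item 2:** "Any non-hematologic grade 3 or greater toxicity (including neurologic toxicity) that is associated with a blood glucose level" of 80 mg/dl or lower, provided it resolves with the low-blood-sugar intervention.
- **Serious, hypoglycemia item:** "Any symptomatic grade 3 or 4 hypoglycemia associated with a non-hematologic grade 3 or greater toxicity that is not resolved with" that intervention, and which the investigator considers at least possibly attributable to study drug.
- **Serious, death item:** a grade 5 toxicity at least possibly attributable to study drug.

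Appendix VII sets grade 3 hypoglycemia at "<40-30 mg/dL; <2.2-1.7 mmol/L" and grade 4 below 30 mg/dl, or with life-threatening consequences or seizures.

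In the pilot, 6 of 10 patients with a concerning toxicity, or 1 of 10 with a serious one, triggers a dose reduction, and termination if it recurs at the reduced dose (5.3.1, 9.3.1). After a serious toxicity, "all other patients currently on treatment will either be dose reduced immediately (if on full dose glyburide) or stop glyburide immediately" if already on the reduced dose (5.3.1.2). Under 5.4.2, with no serious toxicities, 3 or fewer concerning toxicities in the pilot lead to once-daily fingersticks in the randomized portion. With 4 or 5, "patients in the Randomized Portion of the trial will be taught and instructed to measure blood glucose as per section 5.4.1", which means four times daily to one week after SRS. The only toxicity ground for stopping drug in 4.1.9 is "A dose limiting toxicity (DLT) is reached"; 4.2.9 matches it.

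**The concern.** A patient at 35 mg/dl without symptoms has a DLT and stops the drug. The same glucose with symptoms has to clear further hurdles before it counts, and may clear none. That is the wrong way round for a pilot whose primary endpoint is DLT occurrence and whose size, according to 9.5.1.3, was chosen to check that hypoglycemia rates are acceptable.

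Three things depend on the classification:

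- **The pilot decision.** Dose reduction, termination and the randomized-portion fingerstick schedule all depend on the count.
- **The individual patient.** Without a DLT, neither 4.1.9 nor 4.2.9 requires the drug to stop.
- **Later monitoring.** A patient with no concerning or serious toxicity at one week drops to once-daily fingersticks in the pilot (4.1.6.4). In the randomized portion the patient is told to stop monitoring (4.2.6.4). Drug continues to the one-month MRI.

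The effect on the count is limited to events after SRS, because 7.1.4 and 7.2.3 make a patient with a pre-SRS DLT inevaluable. Before SRS, the wording decides whether the patient is removed or stays on drug.

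**Working it through.** **The plan's own figures (9.5.1, n = 10, exact binomial)**

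- Serious rule, 1 or more: at 30%, 1 − 0.70^10 = 0.9718 (stated 97%); at 1%, 0.99^10 = 0.9044 (stated 90%).
- Concerning rule, 6 or more: P(X ≤ 5 | 10, 0.30) = 0.9527 (stated 95%); P(X ≥ 6 | 10, 0.70) = 0.8497 (stated 85%).

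All four reproduce. They describe the rate of *counted* events, so what matters is which events are counted.

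**Enumeration.** Take a non-fatal, symptomatic grade 3-4 hypoglycemia. Three yes/no facts settle its class: a separate non-hematologic grade 3+ toxicity, resolution with intervention, and at least possible attribution. That gives 2 × 2 × 2 = 8 profiles. There are two readings:

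- **A:** the grade 3+ toxicity must be separate from the hypoglycemia.
- **B:** the hypoglycemia itself qualifies.

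C = concerning, S = serious, – = not a DLT. *After* means with *asymptomatic* deleted from item 1, and S taking precedence where both apply.

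| Separate grade 3+ | Resolved | Possibly attributable | A now | B now | A after | B after |
|---|---|---|---|---|---|---|
| yes | yes | yes | C | C | C | C |
| yes | yes | no | C | C | C | C |
| yes | no | yes | S | S | S | S |
| yes | no | no | – | – | C | C |
| no | yes | yes | – | C | C | C |
| no | yes | no | – | C | C | C |
| no | no | yes | – | S | C | S |
| no | no | no | – | – | C | C |

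Totals:

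- Now, A: 2 C + 1 S + 5 uncounted = 8.
- Now, B: 4 C + 2 S + 2 uncounted = 8.
- After, A: 7 C + 1 S + 0 uncounted = 8.
- After, B: 6 C + 2 S + 0 uncounted = 8.

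Every asymptomatic grade 3-4 profile counts under item 1 on both readings, whatever its attribution.

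**Effect at the thresholds** (events after SRS in evaluable patients):

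- Five asymptomatic patients plus one symptomatic, resolved, with grade 1-2 symptoms: 5 + 0 = 5 of 10 on A, no automatic reduction; 5 + 1 = 6 of 10 on B or after the change, dose reduction.
- Three plus one of the same kind: 3 on A, once-daily fingersticks in the randomized portion; 4 on B or after the change, four times daily.
- One unresolved, possibly attributable event with grade 1-2 symptoms: 0 serious on A, 1 serious and an immediate dose reduction on B. The change does not alter this contrast (see the remedy).

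**The case against.** The best defence is reading B. Hypoglycemia is a graded CTCAE event and is not hematologic, so item 2 taken literally already catches a symptomatic event that resolves. Sections 9.5.1.1 and 9.5.1.3 describe the rules in terms of grade 3 hypoglycemia and of concerning hypoglycemia, which fits B. What B leaves out is narrow: glucose below 40 mg/dl, symptoms, failure of a repeatable intervention, and a judgement that the drug is not even possibly responsible, when 1.8 names hypoglycemia as its most common side effect. Not counting an event judged unrelated is also a defensible principle.

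B is arguable, and on B the gap is small. But B makes the serious item's requirement for an associated grade 3+ toxicity redundant, and the loose wording in 9.5.1 does not settle the matter. The attribution principle is also not applied consistently: an asymptomatic event counts whatever its cause.

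Other points stand in part:

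- The eight profiles are unweighted and not independent. An unresolved event below 40 mg/dl leads to a call to the study team or 911 (5.4.1), and often to care that is itself graded 3 or 4 under Appendix VII, so the third threshold example is somewhat strained.
- Five of 10 avoids only the automatic reduction. The DSMQAC must still approve the pilot data (5.2).
- Section 5.3.1 says DLT patients stay evaluable, which conflicts with 7.1.4. The specific pre-SRS rule is taken to govern here.
- Backstops exist: symptom-triggered glucose checks (Appendix II), monthly AE and 24-hour SAE reporting (7.3.1), and unblinding on request in a life-threatening event, which ends treatment (7.6). None adds the event to the DLT count, and none requires stopping because of the event itself.

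**Conclusion.** The concern holds on either reading. Symptomatic grade 3-4 hypoglycemia is held to stricter conditions than asymptomatic, and some of it meets no DLT item: 5 of 8 profiles if a separate grade 3+ toxicity is required, 2 of 8 if the hypoglycemia itself qualifies. The two that survive both readings are unresolved and judged not attributable.

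The practical size is unknown. The documents give neither a rate of grade 3-4 hypoglycemia nor the share that is symptomatic, so no probability of a changed decision can be given. One patient is enough to change the outcome when the count stands at a threshold. The count examples assume events after SRS in evaluable patients. This should be fixed, because it concerns the pilot's primary endpoint and a mandatory drug stop.

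**What to change.** Delete *asymptomatic* from concerning item 1 in 5.3.1, 5.3.2 and both parts of 7.3.4. Every grade 3-4 hypoglycemia is then at least a concerning toxicity and the patient stops the drug. The existing most-severe-toxicity rule moves the event to serious where those criteria are met. That rule is written for patients with several toxicities, so it would help to say that it also covers one event meeting two definitions.

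One profile stays ambiguous in class: unresolved, possibly attributable, with no separate grade 3+ toxicity. It would be concerning on A and serious on B, but it would count and stop the drug either way. A sentence saying whether hypoglycemia is itself a qualifying non-hematologic toxicity would settle it.

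The cost is one word in four places. Glucose logs and AE evaluations already collect the data. The downside is a possibly higher DLT count and more discontinuations, of a size the documents do not allow anyone to estimate.

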7.4 Drug/Placebo Supply and Ordering

This protocol will use the Investigational Drug Services (IDS) pharmacy at UAB. The IDS pharmacy will be the only people unblinded to the study's investigational medication for the Randomized Portion of the study. The rest of the study team including treating physicians and patients will be blinded to the investigational medication.

Glyburide and the placebo will both be available by commercial/generic supply. Please note the placebo pill is not a sugar pill.

IDS will hold a supply of glyburide and placebo and dispense as appropriate when patients are enrolled on study. Once a patient is enrolled, a prescription for either glyburide or investigational medication will be faxed to the IDS pharmacy. Once the investigator has been verified by IDS, the drug will be dispensed. A sufficient supply of glyburide or investigational medication will be dispensed for the patient's entire study participation (beginning at least 5 days prior to SRS and continuing till the evening dose of the one month post SRS MRI scan). The investigational medication, when dispensed, will be packaged in a way that will keep the study team and patient blinded (for the Randomized Portion of the study). Once prepared by the IDS pharmacy the research team will be notified to retrieve the glyburide or investigational medication supply and take it to the patient.

7.4.1 In the event that a dose reduction is required for a patient who is currently on treatment in the Pilot Portion of the study (see Section 7.1) the following will occur. The patient will be notified and asked to return their supply of glyburide immediately. The IDS pharmacy will appropriately catalog (and if applicable destroy) the tablets per institutional guidelines. 0.75 mg glyburide tablets will then be dispensed for the patient. The study team will retrieve the new dose reduced supply of glyburide and provide it to the patient. Further dispensing of glyburide will be at this reduced dose by IDS unless otherwise notified by the study team.

7.5 Initiation of Therapy

All patients that are registered on study and eligible to receive therapy should initiate drug therapy (glyburide on the Pilot Portion or investigational medication on the Randomized Portion) at least 5 days prior to SRS.

7.6 Guidelines and Procedure for Unblinding Treatment (Randomized Portion)

The site/treating physician may request to unblind their patient's treatment randomization only under specific circumstances. All must be done to ensure the blind. The following circumstances would be deemed appropriate for unblinding:

- A life-threatening event or extraordinary clinical circumstance in which knowledge of the drug assignment will affect clinical judgment.

7.6.1 The unblinding procedure is outlined below. All parties must strictly adhere to the procedure in order to maintain protocol integrity and protect the blind.

1. The requesting physician will call and/or email the research team to request the unblinding of their patient.
2. The requesting physician will provide the case number, reason and appropriate details for the request of unblinding.
3. The research team will then determine after consulting with the PI of the study if unblinding is appropriate in the specific case addressed. If unblinding is denied, the reason will be provided in a timely fashion to the requesting physician. An appeal can be made by the requesting physician if appropriate.
4. If approved for unblinding, the IDS pharmacy is contacted by the research team.
5. The IDS pharmacy may be in direct contact with the requesting physician or the research team/PI may be asked to relay the unblinded information to the requesting physician.

All discussions and outcomes of a blinding request will be well documented in the patient's chart as well as in the research office. All research staff involved in the unblinding activity for this protocol should continue to remain blinded to drug assignment/randomization if possible.

7.6.2 The research office will notify the UAB IRB and UAB Clinical Trials Monitoring Committee (CTMC) of patient unblindings at the time of the annual protocol review. If appropriate and fitting the criteria of the Problem Report form, appropriate steps will be taken for reporting.

7.6.3 Unblinded patients will be taken off study treatment and followed for 30 days after last dose of investigational medication, irrelevant to the date of unblinding.

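### Section 7.6.1 puts research-team approval, with possible refusal and no time limit, before emergency unblinding, and its relay option conflicts with 7.4 and with the section's own aim of keeping staff blinded

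*Combined protocol and SAP*

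**What the plan says.** Section 7.6 gives one ground for unblinding in the Randomized Portion: "A life-threatening event or extraordinary clinical circumstance in which knowledge of the drug assignment will affect clinical judgment". Section 7.6.1 sets out the procedure:

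- Step 1: "The requesting physician will call and/or email the research team to request the unblinding of their patient".
- Step 2: the physician supplies the case number and the reason.
- Step 3: "The research team will then determine after consulting with the PI of the study if unblinding is appropriate in the specific case addressed". Refusal is foreseen: "If unblinding is denied, the reason will be provided in a timely fashion to the requesting physician", with a right of appeal.
- Step 4: "If approved for unblinding, the IDS pharmacy is contacted by the research team".
- Step 5: the pharmacy may speak to the physician directly, or "the research team/PI may be asked to relay the unblinded information to the requesting physician".

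The procedure is binding: "All parties must strictly adhere to the procedure in order to maintain protocol integrity and protect the blind". A closing sentence asks that research staff who take part stay blinded themselves, so far as that can be done.

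Elsewhere, 5.2.1 has the IDS pharmacy randomize patients and hold the blind. Section 7.4 states the default: "The IDS pharmacy will be the only people unblinded to the" study medication in the Randomized Portion, with treating physicians, patients and the rest of the study team blinded.

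**The concern.** There are two separate problems.

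The first is the approval step. The protocol itself treats the listed circumstances as appropriate for unblinding, yet the physician facing one must wait for a decision by people who do not hold the code, and that decision can go against the request. The party that can answer at once is reached only at step 4. What is at stake is how quickly the physician learns the assignment when it bears on clinical judgment.

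The second is the relay. Using it gives the assignment to the research team or the PI, who do not need it to manage the patient. Under 7.3.3 the research team, the treating physicians and the PI review toxicities and their attribution. Under 9.1.2 a death in the interval from SRS to the one-month MRI counts as treatment failure if its cause is considered probably or likely related to glyburide. Someone who knows the arm is poorly placed to make or review that judgment.

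**Working it through.** No arithmetic applies, since the point depends on no rate, sample size or error level. The check sets the provisions side by side.

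**1. Is there any route other than research-team approval?** No. Steps 1, 3 and 4 run in sequence, the research team makes the contact with the pharmacy, and strict adherence is required of everyone. There is no direct physician-to-pharmacy request, no emergency exception and no out-of-hours contact.

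**2. Is there a time limit?** No. The only timing phrase in the procedure concerns giving the reason for a refusal. The decision, the appeal and the release of the code have none.

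**3. Who decides?** The research team, after consulting the PI. The PI is a required consultation and not a second approver.

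**4. Is the relay needed?** No. Direct contact between pharmacy and physician is the first alternative in the same step. The research office also needs only the fact of unblinding for its later duties: reporting to the IRB and the monitoring committee (7.6.2), and taking the patient off study treatment with 30 days of follow-up (7.6.3).

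**5. Does the relay conflict with other text?** Yes, whenever it is used.

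| Provision | Who may know the assignment |
|---|---|
| 7.4 | IDS pharmacy only |
| 7.6.1, closing sentence | Research staff involved should stay blinded where they can |
| 7.6.1, step 5, first option | Pharmacy and requesting physician |
| 7.6.1, step 5, second option | Pharmacy, research team or PI, and requesting physician |

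The first option unblinds the requesting physician, which any emergency code break must do. Only the second adds research staff. Because the first option exists, keeping those staff blinded is possible, so the relay defeats the closing sentence without need.

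**6. Does the exposure touch a trial outcome?** It can. Section 7.3.3 names the research team and the PI among those who review toxicities and attribution. Section 9.1.2 makes drug-related death a component of failure and analyzes each patient under the randomized regimen, so an unblinded patient still counts. Section 9.1.2 does not say who judges relatedness to glyburide. Reading it with 7.3.3 is an inference, though the natural one.

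**The case against.** **Section 7.4 is only the default and 7.6 is its exception.** This is fair in part. Read with complete literalness, 7.4 would forbid any emergency code break, because it lists treating physicians among the blinded. But 7.4 does not mention an exception, and an exception for the treating physician would not explain disclosure to the research team. The conflict with 7.6.1's closing sentence remains in any case.

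**Prior review has a purpose.** Step 3 checks that knowing the assignment would affect clinical judgment, and so guards against needless code breaks. That stands as a real benefit and is the cost of the change. It does not explain why the check must come first, with no time limit, in a life-threatening event.

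**A reader might infer that the procedure delays care, above all for severe hypoglycemia.** The documents do not support that. The low-blood-sugar steps in 5.4.1.1 and Appendices II and IV act on glucose and symptoms, and 7.2.2 stops study medication at once for a DLT. Neither needs the code. What can be delayed is disclosure. The objection does not dispose of the point, because the ground in 7.6 is wider than the DLT definition in 5.3.2: a life-threatening event that is not fatal and not linked to low glucose is no DLT.

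**A reader might also infer bias in the steroid component of the primary endpoint and try to put a figure on the change in the probability of a positive screening result.** That does not hold either. Under 8.2.1 the steroid decision is the treating physician's and also requires symptoms and imaging evidence of increasing edema. The requesting physician learns the arm under the present text and under the fix, so the relay makes no difference to that decision.

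**Conclusion.** The point holds on the text, as a matter of procedure. For circumstances the protocol already accepts as grounds for unblinding, 7.6.1 allows no route except a research-team decision that can be refused and has no time limit, and this can delay disclosure of the assignment. The relay in step 5 cannot be squared with 7.4 or with the closing sentence of 7.6.1, and it can needlessly unblind people who review attribution. The passages must be reconciled.

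The conclusion has limits. The relay is one of two options, so the extra unblinding occurs only if it is used. Delay is inferred from the added steps and the missing time limit; the documents give no durations. They also give no expected number of unblindings, so no effect on the trial's error rates or on the probability of a positive screening result can be stated, and none is claimed. This is a cheap improvement and not a threat to the trial's validity.

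**What to change.** - **7.6.1, steps 1 to 4:** for the circumstances 7.6 already lists, the requesting physician asks the IDS pharmacy directly, giving the case number and reason, and the pharmacy releases the assignment to that physician on request. Say how the pharmacy is reached, including out of hours, since the documents are silent on this.
- **7.6.1, step 5:** delete the relay through the research team or PI.
- **Afterwards:** tell the research team and PI only that unblinding took place, and review the justification then. The documentation required by 7.6.1 and the reporting in 7.6.2 already provide the record.
- **7.4:** name 7.6 as the exception, limited to the requesting physician.

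The cost is a wording amendment, plus the occasional unblinding that prior review might have prevented. The change does not protect the requesting physician's own later judgments, since that physician knows the arm after any code break. It removes only the avoidable exposure of the research team and PI. No dose, monitoring rule or analysis changes.
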